- Immunosuppressants or other immune-modifying drugs administered chronically (i.e. >14 days in total) up to the last blood sampling. For corticosteroids, this will mean prednisone ≥ 20 mg/day, or equivalent. Inhaled and topical steroids are allowed.
- Long-acting immune-modifying drugs administered at any time during the study period up to the last blood sampling (e.g. infliximab).
- A vaccine not foreseen by the study protocol administered during the period starting 30 days before and ending 30 days after the last dose of study vaccine administration.
In case an emergency mass vaccination for an unforeseen public health threat (e.g.: a pandemic) is organized by the public health authorities, outside the routine immunization program, the time period described above can be reduced if necessary for that vaccine provided it is licensed and used according to its Prescribing Information and according to the local governmental recommendations and provided a written approval of the Sponsor is obtained.
- Immunoglobulins and/or any blood products administered during the study period up to the last blood sampling.
- Receipt of a vaccine against HZ or VZV or pneumococcal vaccine other than the study vaccine during the study period.

CONFIDENTIAL204487 (ZOSTER-059 PRI)
Protocol Amendment 2 Final**6.8. Intercurrent medical conditions that may lead to elimination of a subject from per-protocol analyses**

At each study visit subsequent to the first vaccination/the vaccination visit, it must be verified if the subject has experienced or is experiencing any intercurrent medical condition (IMC). If it is the case, the condition(s) must be recorded in the eCRF. An IMC is defined as a condition that has the capability of confounding the immune response to the study vaccine or its interpretation. Subjects may be eliminated from the Per-protocol cohort for immunogenicity if, during the study, they incur an IMC.

Examples of IMCs include cases of HZ or a confirmed or suspected immunosuppressive or immunodeficient condition resulting from disease (e.g., malignancy, HIV infection).

All IMCs including HZ will be recorded until Visit Month 3 for subjects in the Co-Ad group and Visit Month 5 for subjects in the Control group. All IMCs will be recorded in AE/SAE screens as appropriate.

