9.2. Subject withdrawal

Withdrawals will not be replaced.

CONFIDENTIAL204487 (ZOSTER-059 PRI)
Protocol Amendment 2 Final**9.2.1. Subject withdrawal from the study**

From an analysis perspective, a ‘withdrawal’ from the study refers to any subject who did not come back for the concluding visit/was not available for the concluding contact foreseen in the protocol.

All data collected until the date of withdrawal/last contact of the subject will be used for the analysis.

A subject is considered a ‘withdrawal’ from the study when no study procedure has occurred, no follow-up has been performed and no further information has been collected for this subject from the date of withdrawal/last contact.

Investigators will make an attempt to contact those subjects who do not return for scheduled visits or follow-up.

Information relative to the withdrawal will be documented in the eCRF. The investigator will document whether the decision to withdraw a subject from the study was made by the subject himself/herself, or by the investigator, as well as which of the following possible reasons was responsible for withdrawal:

- Serious adverse event.
- Unsolicited non-serious adverse event.
- Solicited adverse event
- Protocol violation (specify).
- Consent withdrawal, not due to an adverse event*.
- Moved from the study area.
- Lost to follow-up.
- Other (specify).

*In case a subject is withdrawn from the study because he/she has withdrawn consent, the investigator will document the reason for withdrawal of consent, if specified by the subject, in the eCRF .

Subjects who are withdrawn from the study because of SAEs/AEs must be clearly distinguished from subjects who are withdrawn for other reasons. Investigators will follow subjects who are withdrawn from the study as result of a SAE/AE until resolution of the event (see Section [8.5.1.2](#)).

CONFIDENTIAL204487 (ZOSTER-059 PRI)
Protocol Amendment 2 Final**9.2.2. Subject withdrawal from study vaccine(s)**

A 'withdrawal' from the study vaccine(s) refers to any subject who does not receive the complete treatment, i.e. when no further planned dose is administered from the date of withdrawal. A subject withdrawn from the study vaccine(s) may not necessarily be withdrawn from the study as further study procedures or follow-up may be performed (safety or immunogenicity) if planned in the study protocol.

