5.2. Criteria for eliminating data from Analysis Sets

Elimination codes are used to identify subjects to be eliminated from analysis. Detail is provided below for each set.

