5.2.4. Elimination from Per-protocol analysis Set (PPS)

A subject will be excluded from the PPS analysis under the following conditions:

Code	Condition under which the code is used	Visit (timepoints) where the code is applicable	Applicable for analysis set
900	Invalid informed consent or fraudulent data. Subjects excluded from all stat analysis Note: Subjects receiving a code 900 should not receive any other elimination codes.	All	All
1010	Vaccine number not allocated Note: Subjects receiving a code 1010 should not receive any other elimination codes	Day 1	Randomized Set, ES, PPS
1030	Study vaccine not administered AT ALL but subject number allocated Note: Subjects receiving a code 1030 should not receive any other elimination codes	Day 1	ES, PPS
1040*	Administration of concomitant vaccine(s) forbidden in the protocol Comment: Co-Ad group: From 30 days before 1st vaccination up to Month 3 blood sampling Control group: From 30 days before 1st vaccination up to Month 5 blood sampling	Co-Ad group: Day -30 to Month 3 Control group: Day -30 to Month 5	PPS
1050	Randomization failure (subject not randomized in the correct group) Comment: To check for manual randomisation, treatment not compatible with one assigned by SBIR	Day 1	PPS
1070	 Side, site or route of study vaccine administration wrong or unknown Administration not according to protocol for reason specified by the investigator, other than side, site and route Wrong replacement or study vaccine administered (not compatible with the vaccine regimen associated to the treatment number) Administered study vaccine reported as being the correct one but is not compatible with the vaccine regimen associated to the treatment number. 	Co-Ad group – Day 1, Month 2 Control group – Day 1, Month 2, Month 4	PPS
1080	Vaccine has been administered (effective treatment number) despite a temperature deviation qualified by Status QA GMP NON Use	Co-Ad group – Day 1, Month 2 Control group – Day 1, Month 2, Month 4	PPS
1090	Expired vaccine administered	Co-Ad group – Day 1, Month 2 Control group – Day 1, Month 2, Month 4	PPS
2010	Protocol violation (inclusion/exclusion criteria)	Day 1	PPS
2040*	Administration of any medication forbidden by the protocol Co-Ad group: From 1st vaccination up to Month 3 blood sampling Control group: From 1st vaccination up to Month 5 blood sampling	Co-Ad group – Day 1 up to Month 3 Control group – Day 1 up to Month 5	PPS

204487 (ZOSTER-059 PRI) Statistical Analysis Plan Amendment 3

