2120	Obvious incoherence or abnormality or error in data (incoherence between CRF and results, wrong labelling) Comment: Co-Ad group: Check for above condition on anti-gE	Co-Ad – Month 1, Month 3 Control – Month 1, Month 5	PPS		
	serological result at Month 3 and on pneumococcal serological results at Month 1				

204487 (ZOSTER-059 PRI) Statistical Analysis Plan Amendment 3

Code	Condition under which the code is used	Visit (timepoints) where the code is applicable	Applicable for analysis set
	Control group: Check for above condition on anti-gE serological result at Month 5 and on pneumococcal serological results at Month 1		
2500	Incomplete vaccination course. Comment: The subject should receive one dose of Prevenar 13 vaccine and 2 doses of Hz/su vaccine	Co-Ad – Day 1, Month 2 Control – Day 1, Month 2, Month 4	PPS

BS = Blood sample

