6.1.2. Additional considerations

- The following additional tables will be generated:
 - The number of subjects enrolled into the study as well as the number of subjects excluded from PPS analyses will be presented through two consort tables:
 - Consort table 1 Showing the subjects disposition from Enrolled Set to Randomized Set
 - Consort table 2 Showing the subjects disposition from Randomised Set to *Per Protocol Set for immunogenicity*
 - Withdrawal status will be summarized by group. The numbers of withdrawn subjects will be tabulated according to the reason for withdrawal

^{*} Attribution of these elimination codes are responsibility of CRDL following review of individual data listings

204487 (ZOSTER-059 PRI) Statistical Analysis Plan Amendment 3

- The following table will be generated for CTRS:
 - Percentage of Enrolled subjects by country will be tabulated by group.
 - Percentage of Enrolled subjects in the following age categories ≤64, 65-84, ≥85 will be tabulated by group.
- For computation of age, following rule need to be considered:
 - Age will be calculated as the number of years between the date of birth and the date of first vaccination.
 - To ensure that the collection of date of birth will not jeopardise the privacy of Personally Identifiable Information (PII), only a partial date of birth (MMYYYY) will be collected.
 - Therefore, the 15th of the month will be used to replace the missing date.
 - In case the month is missing, the date will be replaced by the June 30th of the year.
- Summary of important protocol deviations leading to elimination will be presented.

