Number of subjects vaccinated	XXX	XXX	XXX
End of study status			
[EACH CATEGORY]	XXX	XXX	XXX
Reasons for withdrawal:			
[REASONS]	XXX	XXX	XXX

Co_Ad = Dose 1: Prevenar 13 + HZ/su, Dose 2: HZ/su

Control = Dose 1: Prevenar 13, Dose 2: HZ/su, Dose 3: HZ/su

Vaccinated = number of subjects who were vaccinated in the study

Completed = number of subjects who completed <end of active phase visit, last study visit>
Withdrawn = number of subjects who did not come for the <end of active phase visit, last study visit>
Unknown = number/percentage of subjects who have not come for the <end of active phase visit, last study visit> yet

Template 6 Visit attendance < Exposed set>

		<each< th="">group> N=XXX	</each<>	group> N=XXX
Visit	Status	n	%
INFORMED CONSENT	Completed		
RANDOMIZATION	Completed		
<each visit=""></each>	Attended		
	Not attended yet		
	Permanent discontinuation prior to this visit		
	Not attended		
CONCLUSION	Completed		

Co Ad = Dose 1: Prevenar 13 + HZ/su, Dose 2: HZ/su

Control = Dose 1: Prevenar 13, Dose 2: HZ/su, Dose 3: HZ/su

N = Number of subjects in each group or in total

Conclusion = date of last visit or withdrawal

204487 (ZOSTER-059 PRI) Statistical Analysis Plan Amendment 3

Template 7 Summary of important protocol deviations leading to elimination from any analyses

Category Sub-category	•	<each group=""> N=XXXX</each>			Total N=XXXX		
	осс	n	%	осс	n	%	
At least one important protocol	XXX	XXX	XX.X	XXX	XXX	XX.X	
deviation							
<category 1=""></category>	XXX	XXX	XX.X	XXX	XXX	XX.X	
	XXX	XXX	XX.X	XXX	XXX	XX.X	
	XXX	XXX	XX.X	XXX	XXX	XX.X	
<category 2=""></category>	xxx	XXX	XX.X	xxx	XXX	XX.X	

Co Ad = Dose 1: Prevenar 13 + HZ/su, Dose 2: HZ/su

Control = Dose 1: Prevenar 13, Dose 2: HZ/su, Dose 3: HZ/su

N = Total number of subjects

Occ = number of occurrences = number of important protocol deviations

n/% = number / percentage of subjects with important protocol deviations

Template 8 Percentage of subjects with serological results who were eliminated from PPS for immunogenicity

	[each group]
Number of subjects in Exposed Set with serological results available	
Number of subjects with serological results eliminated from PPS for immunogenicity	
Percentage of subjects with serological results eliminated from PPS for immunogenicity	

Co Ad = Dose 1: Prevenar 13 + HZ/su, Dose 2: HZ/su

Control = Dose 1: Prevenar 13, Dose 2: HZ/su, Dose 3: HZ/su

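### One subject-level per-protocol set serves both vaccines, so, read literally, events after the Month 1 sample can remove a valid MOPA titre from the primary Family 3 comparison, over a window that closes later in Control

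*SAP*

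**What the plan says.** SAP 5.1.4 defines a single PPS for immunogenicity, and SAP 6.3.1 makes it the primary analysis set. The Family 3 endpoint is the MOPA titre at Visit Month 1 in both groups (SAP 4.1).

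Elimination is worded by subject. SAP 5.2 states: "Elimination codes are used to identify subjects to be eliminated from analysis". SAP 5.2.4 opens its table with "A subject will be excluded from the PPS analysis under the following conditions". Code 2500 in that table comments: "The subject should receive one dose of Prevenar 13 vaccine and 2 doses of Hz/su vaccine". It is checked at Day 1 and Month 2 in Co-Ad, and at Day 1, Month 2 and Month 4 in Control. Template 8 has one line per group for "Number of subjects with serological results eliminated from PPS for immunogenicity", with no split by visit or antigen.

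Codes 1040 and 2040 to 2070 run up to the Month 3 sample in Co-Ad and the Month 5 sample in Control. They are discretionary. The table footnote says "Attribution of these elimination codes are responsibility of CRDL following review of individual data listings" (the CRDL is the Clinical Research and Development Lead), and Protocol 6.8 says "Subjects may be eliminated from the Per-protocol cohort for immunogenicity if, during the study, they incur an IMC".

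Some text points the other way or is ambiguous. The table has a column headed "Visit (timepoints) where the code is applicable", and Protocol 9.2.1 says "All data collected until the date of withdrawal/last contact of the subject will be used for the analysis". Code 2100 eliminates only when all post-vaccination results are missing, so a missing Month 3 or Month 5 result alone does not remove anyone. The Exposed Set analysis is run whatever the exclusion rate (SAP 6.3.1 and 9), and Template 31 gives the MOPA ratios on it.

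**The concern.** A dose missed or a sample mistimed after Month 1 cannot alter a titre that has already been drawn. If such events remove the subject, the primary Family 3 population is conditioned on what happens after the endpoint is measured. The opportunity for this also differs by arm: after Month 1, Co-Ad has one further vaccination visit and nominally two months to its last sample, while Control has two visits and four months.

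The codes that can act in this way are:

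- 1070 to 1090: administration, storage or expiry fault at Month 2 or 4
- 2080: a later vaccination interval
- 2090 and 2120: an off-window or incoherent Month 3 or 5 sample
- 2500: an incomplete HZ/su course
- 1040 and 2040 to 2070: a later forbidden vaccine, medication, condition or infection, if the CRDL attributes the code

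The asymmetry does not run in one direction only. The Dose 1 to Dose 2 rule is stricter in Co-Ad, which has an 83-day upper limit where Control has none.

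At stake are a small selection effect on 13 ratios that must all pass for the trial to be conclusive, and the loss of some valid Month 1 data.

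**Working it through.** **1. The plan's own figure.** Inputs are from SAP Table 4 (Protocol Table 23): 410 per group, one-sided alpha 2.5%, margin log10(2) = 0.301, true ratio 1, and 13 SDs from 0.644 to 1.094. For each serotype, beta is the probability that a noncentral t with 2n − 2 degrees of freedom and noncentrality 0.301 / (SD × √(2/n)) falls below its 97.5% critical value. The sum over 13 serotypes is 9.04%, against 8.98% from adding the stated Family 3 betas. Power for Families 1 and 2 exceeds 99.99%. The stated global power of about 91% therefore reproduces.

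**2. When the codes stop applying.** Inputs are the intervals in SAP 5.1.4, counted from Day 1 for compliant subjects.

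| | Co-Ad | Control |
|---|---|---|
| Last coded sample, earliest | 49 + 28 = day 77 | 60 + 49 + 28 = day 137 |
| Last coded sample, latest | 83 + 48 = day 131 | no limit (Dose 1 to Dose 2 has only a 60-day minimum) |
| Month 1 sample (day 28 to 48) to last sample | 77 − 48 = 29 to 131 − 28 = 103 days | at least 137 − 48 = 89 days |

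The windows open together and are shared up to the Co-Ad Month 3 sample. They then close later in Control.

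**3. Data that could be recovered.** Protocol 10.3 allows about 10% non-evaluable (456 enrolled, 410 evaluable per group) but does not give timing or causes, so only a range is possible. The upper bound of 456 is not attainable, because Day 1 codes and bad baseline or Month 1 samples would not be recovered.

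| MOPA N per group | Sum of betas | Beta for 23F |
|---|---|---|
| 410 | 9.04% | 2.41% |
| 420 | 7.89% | 2.15% |
| 430 | 6.89% | 1.92% |
| 440 | 6.01% | 1.71% |
| 456 | 4.83% | 1.42% |

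Global power thus lies between about 91% and at most about 95%.

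**4. Possible shift in the GMT ratio.** Assumptions, none of them from the documents: the fraction lost after Month 1 is in the nominal 1:2 ratio of time (Co-Ad to Control); the tendency to be lost has correlation r of 0.1 to 0.3 with log titre, with the same sign in both arms; and the Table 4 SDs are not reduced for the model covariates. With h(p) = φ(z_p) / (1 − p), where z_p is the standard normal p-quantile,

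shift = 10^( r × SD × [h(p_Control) − h(p_Co-Ad)] ).

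| Loss Co-Ad v Control | h difference | r, SD | log10 shift | Factor | Share of margin |
|---|---|---|---|---|---|
| 2% v 4% | 0.0898 − 0.0494 = 0.0404 | 0.1, 0.644 | 0.0026 | 1.006 | 0.9% |
| 2.5% v 5% | 0.1086 − 0.0599 = 0.0486 (rounded) | 0.3, 1.094 | 0.0160 | 1.037 | 5.3% |
| 5% v 10% | 0.1950 − 0.1086 = 0.0864 | 0.3, 1.094 | 0.0284 | 1.067 | 9.4% |

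Reversing the sign of r inverts the factor. A simulation with 4 million draws gave 1.006 and 1.068 for the first and last rows.

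**The case against.** The strongest reply is that the codes are meant to act by timepoint. The title of SAP 5.2 speaks of eliminating data, not subjects. The timepoint column was added on purpose in SAP Amendment 1. Codes 2100 and 2120 are checked by antigen and visit, and 2100 keeps a subject who has only Month 1 results. Template 8 is an illustrative display and weak evidence of the level at which codes apply. All of this is fair, and it makes the text ambiguous. It does not settle the point, because no sentence says that Month 1 data stay in the PPS once a later code applies.

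A single regimen-compliant cohort is also a legitimate pre-specified choice, particularly when all families must succeed. That stands as a reason to keep this PPS for Families 1 and 2. It does not explain why a later HZ/su fault should govern the Month 1 pneumococcal endpoint.

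The unconditional Exposed Set analysis is a direct cross-check and earns credit, but the decision still rests on the PPS.

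Finally, the shift range is built on assumptions. Its upper end places Control's whole planned 10% loss after Month 1, although that allowance also covers bad samples, and the SDs ignore baseline adjustment. It should be read as illustrative, with the upper end generous.

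**Conclusion.** The point holds on a literal reading of SAP 5.2.4: the primary Family 3 set can depend on events after the endpoint, over a window that closes later in Control. It is an improvement worth making rather than an error. No stated figure is wrong, nothing is lost against the planned power, and the design is not invalidated. The plausible shift in a GMT ratio is a factor of about 1.01 to 1.07 either way against a margin of 2, conditional on the assumed loss fractions and correlations. The net direction is unknown. If the sponsor intends codes to act by timepoint, the selection concern largely disappears, but the SAP must then say so.

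**What to change.** Before database lock, state in SAP 5.2.4 whether a later code removes Month 1 MOPA data, and define a Month 1 PPS for Family 3 using:

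- codes 900, 1010, 1030, 1050 and 2010 as they stand;
- 1070 to 1090 and 2500 for Day 1 only, so that a subject who did not receive every vaccine assigned at Day 1 is still excluded (1030 covers only subjects given no vaccine);
- 2090 for the Dose 1 to Month 1 sample interval only;
- 2100 and 2120 for Month 1 pneumococcal results;
- 1040 and 2040 to 2070, with CRDL review, for onset up to the Month 1 sample.

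Keep the existing PPS for Families 1 and 2 and the Exposed Set analysis for all three. State in SAP 9 that denominators differ between families.

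The cost is SAP wording, one extra population flag and review of the CRDL-attributed codes by onset date. No new data are needed. The downside is the differing denominators.

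A separate slip, which does not bear on this argument, can be corrected at the same time. For Co-Ad, code 2090 pairs Dose 2 with the Month 1 sample, whereas SAP 5.1.4 and Template 9 pair it with Month 3. It should read Month 3.

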5.3. Important protocol deviation not leading to elimination from per-protocol analysis set

For information on important protocol deviation not leading to elimination from the PPS set, refer to the study protocol deviation and management plan (PDMP).

6. STATISTICAL ANALYSES

Note that standard data derivation rule and stat methods are described in Section 12 and will not be repeated below. All analyses will be presented by study phase when there are data for both active and follow up phases.

6.1. Demography

6.1.1. Analysis of demographics/baseline characteristics planned in the protocol

Demographic characteristics (age at first vaccination, sex, race and ethnicity) will be tabulated per treatment group.

The mean age (plus range and standard deviation [SD]) of the subjects, as a whole, and per treatment group will be calculated for ES and PPS. The distribution of subjects enrolled among the study sites will be tabulated, as a whole, and per treatment group.

The same tabulations might be performed by age strata (50-59, 60-69 and \geq 70 YOA) if deemed necessary.

6.1.2. Additional considerations

- The following additional tables will be generated:
 - The number of subjects enrolled into the study as well as the number of subjects excluded from PPS analyses will be presented through two consort tables:
 - Consort table 1 Showing the subjects disposition from Enrolled Set to Randomized Set
 - Consort table 2 Showing the subjects disposition from Randomised Set to *Per Protocol Set for immunogenicity*
 - Withdrawal status will be summarized by group. The numbers of withdrawn subjects will be tabulated according to the reason for withdrawal

^{*} Attribution of these elimination codes are responsibility of CRDL following review of individual data listings

204487 (ZOSTER-059 PRI) Statistical Analysis Plan Amendment 3

- The following table will be generated for CTRS:
 - Percentage of Enrolled subjects by country will be tabulated by group.
 - Percentage of Enrolled subjects in the following age categories ≤64, 65-84, ≥85 will be tabulated by group.
- For computation of age, following rule need to be considered:
 - Age will be calculated as the number of years between the date of birth and the date of first vaccination.
 - To ensure that the collection of date of birth will not jeopardise the privacy of Personally Identifiable Information (PII), only a partial date of birth (MMYYYY) will be collected.
 - Therefore, the 15th of the month will be used to replace the missing date.
 - In case the month is missing, the date will be replaced by the June 30th of the year.
- Summary of important protocol deviations leading to elimination will be presented.

